### 9.2.1 Viral Screen

A screening viral screen will be done for HIV 1/2 Antibody, Hepatitis B Virus Surface Antigen, and Hepatitis C Virus Antibody. The results of the viral screen will be listed.

## **9.2.2 Urine Drug Screen and Urine Alcohol Testing**

UDS will test for the following drugs of abuse: amphetamines, barbiturates, cannabinoids, cocaine, opiates, benzodiazepines, and phencyclidine.

Urine alcohol testing may be requested any time during the study. The results of UDS and urine alcohol testing will be listed.

## **9.2.3 Pregnancy and Follicle Stimulating Hormone (FSH) Tests**

A listing will be done for pregnancy and FSH tests. Serum pregnancy test will be done at screening. Urine pregnancy test will be done at each admission to the qualification phase and, if applicable, treatment phase, and at Day 14/early termination. For postmenopausal women, an FSH test will be done at screening.

## **9.3 Vital Signs**

Scheduled time points in the treatment phase for blood pressure, pulse rate, oxygen saturation (SpO2), and respiratory rate will include predose, 0.5, 1, 1.5, 2, 2.5, 3, 4, 5, 6, 8, 12, and 24 hours (±15 minutes) postdose. For EtCO2, scheduled time points in the treatment phase will be recorded pre-dose and at 0.5, 1, 1.5, 2, 2.5, 3, 4, 5, and 6 hours postdose.

Treatment phase vital signs (blood pressure, heart rate, respiratory rate, SpO2) and EtCO2 will be analyzed as minimum, maximum, and final postdose values since the analyses of these extremes are more meaningful than analyses of individual time points. Vital signs will be summarized using descriptive statistics (n, mean, SD, minimum, median, and maximum). All vital signs, including oral temperature, will be listed. Abnormal and clinically significant abnormal findings will be listed.

## **9.4 12-Lead Electrocardiograms**

The ECG variables will include ventricular heart rate and the PR, QRS, QT, and QTcF intervals.

12-Lead ECG data during the treatment phase (absolute values in heart rate and PR, QRS, QT, and QTcF intervals) will be summarized by parameter and visit using descriptive statistics (n, mean, SD, minimum, median, and maximum). Overall ECG interpretation will be summarized (normal; abnormal, non-clinically significant; and abnormal, clinically significant). Abnormal and clinically significant findings in ECG data will be listed.

## **9.5 Physical Examination Findings**

Physical examination includes a review of the following: head, eyes, ears, nose, throat (HEENT), neck, chest, back, abdomen, extremities and neurological function.

Physical examination findings will be presented in a listing by subject and visit.

## **9.6 Columbia-Suicide Severity Rating Scale (C-SSRS)**

The C-SSRS will be used to assess both behavior and ideation that tracks all suicidal events and provides a summary of suicidal ideation and behavior. It assesses the lethality of attempts and other features of ideation (frequency, duration, controllability, reasons for ideation, and deterrents), all of which are significantly predictive of completed suicide.

Two versions of the C-SSRS will be used in this study: the Baseline/Screening version (lifetime history and past 12 months) and the Since Last Visit version. The Screening version of the C-SSRS will be administered at Visit 1 (Screening). The Since Last Visit version of the C-SSRS will be administered at all subsequent assessment times.

The C-SSRS will be listed by subject and visit.

## 10. DATA HANDLING AND PRESENTATION

---

All safety and statistical outputs will be generated using SAS software, version 9.4. Pharmacokinetic outputs will be generated using WinNonlin version 8.0 or higher.

All programs used to generate statistical analyses will be validated according to Altasciences's SOPs.

The analyses described in this plan are considered a priori, in that they have been defined prior to database lock and prior to breaking the blind. Any analyses performed subsequent to database lock and breaking the blind that are not described within the present plan will be considered post hoc and secondary. Post hoc analyses will be labeled as such in the corresponding statistical output and identified in the clinical study report (CSR).

### 10.1 Safety Analysis Presentation

Adverse events and medical history will be classified using the Medical Dictionary for Regulatory Activities (MedDRA) terminology as defined in the study data management plan (DMP).

Prior and concomitant medications will be coded with the World Health Organization Drug Dictionary- Enhanced (WHO-DDE) as defined in the study DMP.

In general, all safety summary tables will be presented for the Safety population. Summaries for AEs will be presented by treatment. Summaries for other safety endpoints will be presented by treatment if the endpoints are measured at the end of each period or by treatment sequence if the endpoints are measured not at the end of each period but at the end of study only.

In general, the data listings will include all randomized subjects up to the point of study completion or discontinuation; exceptions will be listings pertaining to a subset of subjects only (e.g., subjects with protocol deviations) or a subset of records/events (e.g., abnormal laboratory values).

Categorical variables will be summarized using the PROC FREQ procedure. Continuous variables will be summarized using the PROC UNIVARIATE procedure. For natural log (ln)-transformed endpoints, geometric mean, geometric SD, and CV% will also be presented.

The following general comments also apply to all statistical analyses and data presentations:

- Duration variables will be calculated using the general formula: (end date - start date) +1.
- If the reported value of a clinical laboratory parameter cannot be used in a statistical summary table (e.g., a character string is reported for a parameter of the numerical type), a coded value must be appropriately determined and used in the statistical analyses. In general, a value or lower and upper limit of normal range such as '<10' or '≤5' will be treated as '10' or '5' respectively, and a value such as '>100' will be treated as '100'. However, the actual values as reported in the database will be presented in data listings.
- When assessments are repeated for a given time point or performed at unscheduled times, only the result which is the closest to the dosing time will be included in summary tables.

In general, summary statistics for raw variables (i.e., variables measured at the study site or central laboratory) will be displayed as follows:

- Minima and maxima will be displayed to the same number of decimal places as the raw data.
- Means, medians, and quartiles will be displayed to 1 additional decimal place.
- Standard deviations will be displayed to 2 additional decimal places.
- Percentages will be displayed to 1 decimal place. Percentages between 0 and 0.1 (exclusive) will be displayed as '<0.1'.
- P-values will be displayed to 3 decimal places. P-values that are less than 0.001 will be displayed as '<0.001'.

The numbers of decimal places for summary statistics of derived variables (i.e., variables that are not measured by the study site but are calculated for analysis based on other measured variables) will be determined on a case by case basis. In general:

- Minima and maxima will be displayed to the commonly used unit of precision for the parameter.
- Means, medians, quartiles, and confidence limits will be displayed to 1 additional decimal place.
- Standard deviations will be displayed to 2 additional decimal places.

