6.1 Safety Assessments

Safety assessments will include physical examination, C-SSRS, vital signs (i.e., systolic and diastolic blood pressure, pulse rate, respiratory rate, oral temperature, SpO₂), 12-lead ECG, clinical laboratory tests, and AE monitoring. Continuous SpO₂ monitoring and continuous EtCO₂ will be conducted for approximately 6 hours postdose. Additional safety measurements may be performed at the discretion of an investigator for reasons related to subject safety.

An investigator will be present at the clinical site for at least the first 6 hours following each drug administration and will remain available at all times throughout the study.

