6.1.8 Assessment of Respiratory Depression

Capnography alarms will be set to evaluate for respiratory depression and will include:

- An increase in EtCO₂ to >50 mmHg
- A reduction in O₂ saturation to <90%
- A reduction in respiratory rate to <6 breaths per minute

All alarms will be assessed for clinical significance and reported as AEs, as applicable. Supplemental oxygen will be given as medically necessary.

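### SAP 10.1 keeps only the repeat or unscheduled reading closest to dosing and makes no exception for postdose extremes, so a later, worse recorded SpO2, respiratory rate or EtCO2 value can drop out of the minimum/maximum tables

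*SAP*

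**What the plan says.** SAP 10.1 lists conventions under the lead-in "The following general comments also apply to all statistical analyses and data presentations". One of them begins "When assessments are repeated for a given time point or performed at unscheduled times" and concludes that "only the result which is the closest to the dosing time will be included in summary tables". The selection is by time, not by severity.

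SAP 9.3 says that treatment-phase vital signs and EtCO2 "will be analyzed as minimum, maximum, and final postdose values since the analyses of these extremes are more meaningful" than summaries at individual time points. Protocol 8.7.3.2 plans the same minimum, maximum and final values. Neither section refers to the SAP 10.1 convention or exempts the extremes from it. The protocol has no convention of its own for repeats, and SAP section 12, which lists changes from the protocol, does not mention one.

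Two other provisions bear on the point. Protocol 6.1 foresees extra readings: "Additional safety measurements may be performed at the discretion of an investigator for reasons related to subject safety". Protocol 6.1.8 deals with capnography alarms: "All alarms will be assessed for clinical significance and reported as AEs, as applicable". SAP 9.3 also lists all vital signs, with abnormal findings listed as well; the SAP 10.1 convention concerns summary tables only.

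**The concern.** The two SAP sections pull in different directions. SAP 9.3 wants the worst postdose value for each subject and treatment. SAP 10.1 admits one reading from a set of competing readings and picks it by closeness to dosing. After dosing, the closest reading is the earliest, so a repeat that is worse than the reading it follows is set aside.

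The minimum/maximum/final tables are the only planned numerical summary of the SpO2, respiratory rate and EtCO2 measurements by treatment. Safety and tolerability relative to alprazolam and placebo is a secondary objective, and SpO2 and EtCO2 monitoring are named among the safety endpoints. A recorded excursion that is not judged clinically significant, and so does not become an adverse event, could be missing from every summary table and remain only in a listing. Two programmers working from the same SAP could also produce different minimum SpO2 tables.

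**Working it through.** The plan states no figure on this point, so there is none to reproduce. The check applies the rule to the schedule.

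**Inputs**
- Selection rule and scope: SAP 10.1, as quoted above.
- EtCO2 times (SAP 9.3): "recorded pre-dose and at 0.5, 1, 1.5, 2, 2.5, 3, 4, 5, and 6 hours postdose", which is nine postdose readings in 6 hours.
- Blood pressure, pulse, SpO2 and respiratory rate (SAP 9.3): "predose, 0.5, 1, 1.5, 2, 2.5, 3, 4, 5, 6, 8, 12, and 24 hours", which is twelve postdose readings, nine of them in the first 6 hours.
- The readings in step 3 are invented for illustration.

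**Step 1: which reading is retained.** Before dosing, the reading closest to dosing is the last one. This agrees with the baseline definition in SAP 10.3 and is sensible. After dosing, the closest is the earliest, so between a first reading and its repeat the rule keeps the first.

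**Step 2: direction.** Let A be all recorded postdose readings in a period and S the subset that the rule admits. Since S lies within A, min(S) ≥ min(A) and max(S) ≤ max(A). For the values of concern (low SpO2, low respiratory rate, high EtCO2), the table can therefore only be unchanged or closer to normal. It differs only when the worst reading lies outside S. The final postdose value may change too, if the last time point is repeated, but without a fixed direction.

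**Step 3: constructed cases.** SpO2 is 97 at all twelve scheduled times unless stated.

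| Case | Minimum, all readings | Minimum under SAP 10.1 | Difference |
|---|---|---|---|
| 97 at 1.5 h, repeat at 1.6 h is 88 | 88 | 97 | 9 |
| 88 at 1.5 h, repeat at 1.6 h is 97 | 88 | 88 | 0 |
| Unscheduled 86 at 1.75 h, grouped with 1.5 h or given no time point | 86 | 97 | 11 |
| Unscheduled 86 at 1.75 h, competing with the 2 h reading | 86 | 86 | 0 |

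The last two rows use the same data. SAP 9.3 allows 15 minutes either side of each scheduled vital-signs time, and 1.75 h lies at the edge of both the 1.5 h and the 2 h windows. The SAP does not say to which time point an extra reading belongs, so the result depends on a choice it leaves open.

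**Step 4: size.** A period is affected only if a repeat or unscheduled value was recorded, the rule excluded it, and it was more extreme than every retained value. The documents give no frequency for any of these, so no rate can be computed.

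**The case against.** The strongest reply is that the rule was never meant for extremes. SAP 10.1 calls these general comments, and the rule speaks of repeats at a given time point; SAP 9.3 is the specific section, and a subject's minimum is not a time-point result. Table layouts are in a separate document, which may settle the matter. This is a sensible reading and may be the intended one. But the lead-in claims all analyses and presentations, and the SAP text contains no limit.

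Four further points stand:
- If an abnormal first reading prompts the repeat, the rule keeps the abnormal value. Loss needs a repeat worse than the reading before it.
- The rule does not discard every unscheduled reading; some would be the ones kept.
- Clinically significant SpO2, EtCO2 and respiratory-rate events are reported as adverse events (protocol 6.1.4.1 to 6.1.4.3 and 6.1.8) and so enter the adverse event tables. The invented values 88 and 86 are themselves below the 90% alarm limit.
- Using every reading gives more heavily monitored periods more chances to show an extreme.

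A reader might infer from the gaps of 30 to 60 minutes between spot readings that most short respiratory excursions would be lost from the tables because of this rule. The documents do not support that. The gaps belong to the schedule and would exist without the rule. Protocol section 6.1.4 describes continuous monitoring as monitoring for alarms, with EtCO2 and respiratory rate recorded at nominal times, and does not say that alarm values enter the vital-signs data. An excursion for which no off-schedule value was recorded is missed with or without the rule.

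**Conclusion.** The point holds as a conflict between a stated data-handling rule and the planned analysis of extremes. Read literally, SAP 10.1 can remove a later and worse recorded value from the postdose minimum or maximum, and any resulting error in those values runs one way, toward normal. Its size is unknown and may be nil. It rests on two assumptions: that the rule is programmed as written, and that worse repeat or unscheduled values are recorded in the vital-signs data.

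Two stronger conclusions may tempt a reader. One is that the distortion is largest in the treatment with most respiratory events, so that the comparison with alprazolam is biased in a known direction. That would need the number and timing of extra readings by treatment, which the documents do not give. The other is that a respiratory event could vanish from the report. It could not: the values remain in the listings, and events judged clinically significant remain in the adverse event tables. The tables at issue are descriptive, so no primary or secondary hypothesis test, sample size or power figure is touched.

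**What to change.** Amend SAP 10.1, with a cross-reference in SAP 9.3, along these lines: *The closest-to-dosing rule applies to baseline (last value before dosing) and to by-timepoint or by-visit summaries only. The postdose minimum and maximum of vital signs, SpO2, respiratory rate and EtCO2 use all recorded postdose values in the period, including repeat and unscheduled readings.* The same place should say which reading counts as the final postdose value.

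The cost is a sentence or two and a small derivation change; no study procedure changes. The drawback is unequal ascertainment between periods with few and many extra readings. State it in a table footnote and, if wanted, add a version based on scheduled readings only. The change should be made before database lock and unblinding, because SAP section 10 labels analyses outside the plan that are run after that point as post hoc.

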## **10.2 Pharmacokinetic Analysis**

In general, all PK summary tables will be presented for the PK population.

Individual raw PK concentrations will be displayed with the same precision as received from the bioanalytical laboratory.

Precision for individual PK parameters will be displayed as follows:

- $C_{\max}$  and  $AUC_{0-T}$  will be displayed with the same precision as the raw PK concentration data
- Parameters associated with time (i.e.  $T_{\max}$  and  $T_{last}$ ) will be displayed with 2 decimal places

Summary statistics for concentration and PK parameters will be displayed with the same precision as the individual values, with the exception of N and CV% which will be presented with 0 and 1 decimal place, respectively.

## **10.3 Analysis Time Points**

Unless otherwise specified, the baseline value will be defined as the last non-missing evaluation prior to the first dose of study medication in each treatment period.

## **10.4 Methods for Handling Missing Data**

No imputation of missing PD or PK data will be performed.

The occurrence of missing PD data will be minimized by only including subjects who are rousable, and complete PD assessments in the qualification phase. In addition, all reasonable attempts will be made to rouse subjects for completion of the PD assessments in both the

qualification and treatment phases. Missing PD assessments, including reasons for the missing data, will be listed by subject, and examined on a case-by-case basis to determine if these affect subject allocation (i.e., inclusion in the Modified Completer population). If for a given PD measure, the predose value is missing, calculation of CFBmin and TA\_AOE will not be possible, and the subject will not be included in the Modified Completer population for that PD endpoint. If the actual date and/or time of a postdose PD assessment is unknown, but there is a result at that time point, the value will be used in descriptive statistics of treatment by time point summaries, and PD endpoint by treatment summaries but will be excluded from calculation of TA\_AUE and TA\_AOE which need actual time from dose in order to be calculated.

If the actual collection time of a postdose PK sample is unknown, but a valid concentration value has been measured, the sample will be set to missing in the PK analysis and will be presented in listing but excluded from descriptive statistics. Unknown baseline collection times will be handled on a case-by-case basis.

Further details on handling of missing values will be provided in the Subject Allocation and Request to Break the Blind Form.

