8.3 Missing Values

No imputation of missing PD or PK data will be performed.

The occurrence of missing PD data will be minimized by only including subjects who are rousable and complete PD assessments in the Qualification phase. In addition, all reasonable attempts will be made to rouse subjects for completion of the PD assessments in both the Qualification and Treatment phases. Missing PD assessments, including reasons for the missing data, will be listed by subject, and examined on a case-by-case basis to determine if these affect subject allocation (i.e., inclusion in the Modified Completer population). If for a given PD measure, the predose value is missing, calculation of CFB_{min} and TA_AOE will not be possible, and the subject will not be included in the Modified Completer population for that PD endpoint. If the actual date and/or time of a postdose PD assessment is unknown, but there is a result at that timepoint, the value will be used in descriptive statistics of treatment by timepoint summaries, and PD endpoint by treatment summaries but will be excluded from calculation of TA_AUE and TA_AOE which need actual time from dose in order to be calculated.

If the actual collection time of a postdose PK sample is unknown, but a valid concentration value has been measured, the sample will be set to missing in the PK analysis and will be presented in

listing but excluded from descriptive statistics. Unknown baseline collection times will be handled on a case-by-case basis.

Further details on handling of missing values will be provided in the Subject Allocation and Request to Break the Blind Form, and in the Statistical Analysis Plan (SAP).

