#### 4.2.3 Completer Population

All subjects in the Safety population who complete all 5 crossover periods in the treatment phase of the study, and have sufficient data for evaluation of the primary endpoint (based on a blinded review of data prior to database lock) will be included in the Completer population. Subjects who do not have at least 1 observation within 2 hours of  $T_{max}$  for each treatment for Drug Liking VAS will be excluded from the Completer population.

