#### 7.1.1 Subjective Effects Visual Analogue Scales (VASs)

All VASs will be scored on a 100-point scale, as shown in Table 4. The VASs may be administered as bipolar or unipolar scales, as appropriate, and the choice is determined by the nature of the subjective effect being measured. When VASs are administered as bipolar scales, the neutral point equals 50 (e.g., Drug Liking, Overall Drug Liking, Take Drug Again, Drowsiness/Alertness and Relaxation/Agitation VAS). The neutral point will also be labeled with an anchor, such as “neither like or dislike.” When VASs are administered as unipolar scales, the anchors will be presented using text such as “Not at all” (score = 0) to “Extremely” (score = 100; e.g., Good, Bad, High, and Any Effects VASs). Scales that refer specifically to drug (e.g., Drug Liking, Good Effects VAS, Bad Effects VAS, and Any Effects VAS) are not administered at predose.

Table 4: Visual Analog Scale (VAS) Descriptions

Scale Interpretation	Include Predose	Type of Scale	Description	Question Text	Response Anchors
Balance	No	Bipolar	Drug Liking	At this moment, my liking for this drug is	0: Strong disliking 50: Neither like or dislike 100: Strong liking
Balance	No	Bipolar	Overall Drug Liking	Overall, my liking for this drug is	0: Definitely would not 50: Neither would or would not 100: Definitely would
Balance	No	Bipolar	Take Drug Again	I would take this drug again	0: Not at all 50: Neither would or would not 100: Extremely
Positive	Yes	Unipolar	High	At this moment, I am feeling high	
Positive	No	Unipolar	Good Effects	At this moment, I feel good drug effects	
Negative	No	Unipolar	Bad Effects	At this moment, I feel bad drug effects	

Scale Interpretation	Include Predose	Type of Scale	Description	Question Text	Response Anchors
Other	No	Unipolar	Any Effects	At this moment, I can feel any drug effect	
Other	Yes	Unipolar	Feeling Drunk	At this moment, I am feeling drunk	
Other	Yes	Bipolar	Drowsiness/Alertness	At this moment, my mental state is	0: Very drowsy 50: Neither drowsy nor alert 100: Very alert
Other	Yes	Bipolar	Relaxation/Agitation	At this moment, my mental state is	0: Very agitated 50: Neither agitated or relaxed 100: Very relaxed

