## 7.3 Pharmacodynamics Assessment Visit Windows

Predose measures should be no more than 1 hour prior to dosing. Visit windows for VAS and ARCI should be  $\pm 15$  minutes from each postdose time point. MOAA/S will be conducted during the qualification and treatment phases within 1 hour prior to dosing and approximately ( $\pm 15$  minutes) at 0.5, 1, 1.5, 2 hours postdose, and approximately ( $\pm 30$  minutes) at 3, 4, and 6 hours postdose (refer to Appendix A for more details regarding the order of administration).

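### A predose rating missing in one period removes the subject, not the period, from baseline-dependent PD endpoints, and untimed ratings have no nominal-time fallback

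*SAP*

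**What the plan says.** SAP 10.4 rules out imputation of PD data and then gives two specific rules.

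- **Missing predose value.** The trigger is "If for a given PD measure, the predose value is missing", with no statement of how many periods must be affected. CFBmin and TA_AOE are then not calculable, "and the subject will not be included in the Modified Completer population for that PD endpoint". Protocol 8.3 agrees: "the subject will not be included in the Modified Completer population for that PD endpoint".
- **Unknown clock time.** A postdose result with no date or time stays in the time-point and endpoint summaries. It is left out of TA_AUE and TA_AOE, "which need actual time from dose in order to be calculated". No nominal-time substitute is offered.

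Four other places set the context.

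- SAP 10.3, as a default that yields to anything specified elsewhere: "the baseline value will be defined as the last non-missing evaluation prior to the first dose of study medication in each treatment period".
- SAP 7.3: "Predose measures should be no more than 1 hour prior to dosing". Postdose windows there are ±15 minutes for VAS and ARCI. For MOAA/S they are ±15 minutes up to 2 h and ±30 minutes at 3, 4 and 6 h.
- SAP 4.2.3 defines completers as subjects "who complete all 5 crossover periods in the treatment phase of the study" who also have adequate Drug Liking data.
- SAP 7.1.1: "Scales that refer specifically to drug (e.g., Drug Liking, Good Effects VAS, Bad Effects VAS, and Any Effects VAS) are not administered at predose". Nor do Overall Drug Liking and Take Drug Again have a predose rating, according to Table 4.

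**The concern.** A missing predose value makes CFBmin and TA_AOE incalculable in one period. The stated consequence is removal of the subject. The subject's remaining periods, each with its own baseline, then go unused, although neither planned analysis requires that. The mixed model in SAP 7.4 accepts incomplete subjects. The paired t-test and sign test that replace it need only the two periods in the contrast: a missing baseline under GE-IR 200 mg has no bearing on alprazolam minus placebo.

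The untimed-rating rule has a similar flaw on a smaller scale. The visit window already limits the true time to within 15 or 30 minutes of nominal, yet the value is removed from the time average.

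One gap lies next to these. SAP 10.4 does not clearly say what happens when a predose value serves only as a covariate, as it may for High VAS Emax, a key secondary endpoint. There the SAP 10.3 default, which has no time limit, could admit a rating taken after the previous treatment.

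At stake are precision on sedation and time-averaged endpoints, and a clear definition of baseline. The primary endpoint is not at stake.

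**Working it through.** **Base count.** The documents give no missing rate. The only relevant figure is 48 completers (SAP 3.3). Inputs there: mean difference 26.3, SD 18.62, margin 15, correlation 0, one-sided 0.05. Power is not stated.

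- Difference to detect: 26.3 − 15 = 11.3.
- SD at correlation 0: 18.62 × √2 = 26.33.
- Noncentral t at an assumed 90% power gives 48, as stated; the 3.0 mg figures give 42, also as stated.

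The 48 is sized for Drug Liking and serves below only as a count of subjects.

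**Predose rule.** Let q be an assumed chance that a predose rating is missing in a period, independent across five periods.

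- Share of subjects excluded: 1 − (1 − q)^5.
- Periods truly without a baseline: 48 × 5 × q.
- Periods with a baseline also discarded: 240 × [1 − (1 − q)^5] − 240 × q.

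| q | Subjects excluded | Of 48 | Periods without baseline | Periods with baseline also discarded |
|---|---|---|---|---|
| 1% | 4.9% | 2.4 | 2.4 | 9.4 |
| 2% | 9.6% | 4.6 | 4.8 | 18.3 |
| 5% | 22.6% | 10.9 | 12.0 | 42.3 |

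Under period-level exclusion, a paired contrast loses a subject only if one of its two baselines is missing: 1 − (1 − q)² = 2.0%, 4.0% or 9.8%.

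For the mixed model, the generalized least squares variance of alprazolam minus placebo was computed for 48 subjects over the ten listed sequences. The model had treatment and period effects and a random subject effect (within-subject correlation 0 or 0.5), and baselines were missing at random. The ratio of the standard error under the rule to that with only the affected periods dropped was:

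- q = 1%: 1.018 to 1.022
- q = 2%: 1.040 to 1.042
- q = 5%: 1.108 to 1.117

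**Scope.** Protocol Table 7 assigns CFBmin to MOAA/S, and TA_AOE to MOAA/S, Drowsiness/Alertness and Relaxation/Agitation. All are non-key secondary.

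**Untimed ratings.** Assumed liking curve: 50 + 30 × (t/τ) × exp(1 − t/τ), with τ = 1.5 or 3 h, at the Treatment-phase times (0.5 to 10 h, then 24 h). The time average is taken as trapezoid area divided by the span between the first and last rating used. That divisor is an assumption, because the readable text does not define it. The full averages are 55.13 and 61.61.

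| Rating dropped | Change in average, τ = 1.5 h | Change, τ = 3 h |
|---|---|---|
| 0.5 h | −0.40 | −0.08 |
| Any one from 1 to 8 h | at most 0.07 in size | at most 0.04 in size |
| 10 h | +0.39 | +1.21 |
| 24 h (average then ends at 10 h) | +7.05 | +9.80 |

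Using the nominal time when the true time is 15 minutes off costs at most 0.23 point at any rating. The 24 h row depends wholly on the assumed divisor. It has no counterpart for MOAA/S, whose last rating is at 6 h.

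**The case against.** The strongest defence is that the PD population is complete-case by design, so keeping the same subjects in every comparison is deliberate. This does not carry the rule. SAP 4.2.3 and 4.2.4 ask for five completed periods and usable Drug Liking data, not a predose value on every scale in every period.

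A second defence is that the loss will be small, and much of it stands. VAS ratings are computerized, and subjects are confined and supervised. A predose rating cannot be missing because of the drug given in that period, so the issue is mainly precision. Clustering of gaps within subjects would lower the number excluded. SAP 10.4 also provides case-by-case review and refers to a Subject Allocation form that is not among the documents, although its predose sentence is itself unconditional.

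Three stronger readings should be resisted.

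- A reader might infer that SAP 10.3 and 10.4 contradict each other. They do not for CFBmin and TA_AOE: 10.3 opens as a default, and the 1-hour window in 7.3 together with the explicit rule in 10.4 overrides it. What remains is the unaddressed covariate case. For VAS even that risk is probably modest, since Protocol 1.2 says alprazolam effects are back to baseline by 24 h.
- A reader might infer that an untimed 24 h rating inflates TA_AUE several-fold. That needs a particular curve and a divisor the readable text does not supply. The value also still counts toward the time-point and endpoint summaries.
- A reader might conclude that TA_AUE should be voided whenever the final rating is missing. That would discard up to twelve valid VAS ratings for want of one, and it does not follow from the problem.

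**Conclusion.** The point holds as a minor one. Both documents exclude the subject where only a period is affected. That one gap is enough is the plain reading of an unqualified rule with a per-period baseline; the text does not say so expressly. For each period without a baseline, about 3.5 to 3.9 periods with one are discarded as well (42.3/12.0 to 9.4/2.4). The percentages rest on assumed, independent missing rates. At 1% the cost is about 2.4 of 48 subjects and a standard error about 2% larger.

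The primary endpoint, Overall Drug Liking and Take Drug Again are untouched by the predose rule. Whether High VAS Emax is touched is not clear from the wording.

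The untimed-rating rule is close to immaterial at 1 to 8 h and matters chiefly at 10 and 24 h for VAS and ARCI, by an amount that cannot be fixed until the averaging span is known.

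**What to change.** All changes are to SAP wording and should be made before unblinding, with the departure from Protocol 8.3 recorded in SAP section 12.

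- **SAP 10.4, missing predose value:** omit only that period's baseline-dependent record (CFBmin, TA_AOE or covariate-adjusted value) and keep the subject's other periods.
- **SAP 10.4, unknown clock time only:** use the nominal time for TA_AUE and TA_AOE.
- **SAP 10.3:** state that PD baseline is the value from the same period within 1 hour before dosing, as in 7.3, so that a rating from the previous treatment cannot serve as baseline where predose is only a covariate.

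The cost is incomplete-block data for a few subjects, which the mixed model handles and the paired tests handle contrast by contrast, and a timing error no larger than the visit window.
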